9.1.3.2 Self-Controlled Risk Interval (SCRI)

Retrospective (multi)-database case-only study including subjects who were vaccinated with <<COVID-19 vaccine>> and experienced << event>>.

The risk and control windows should be pre-specified. The incidence rate ratio between a period of time hypothesized to be at increased risk due to exposure (“risk window”) and control window (a pre-specified time window occurring after the risk window) is calculated. The SCRI is a subtype of the SCCS design, with a pre-specified duration of the control period (Figure 4).

Figure 4. Self-Controlled Risk Interval design

[figure not shown]

Note: Example with a risk period of 42 days and a control period of 42 days

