9.2.2 Study Period, Population and Follow-up Period

The study population will comprise all persons in the source population that are eligible for the study according to specific inclusion and exclusion criteria (such as study period, design requirements and exclusion of prior events, see generic conditions in **Table 3**).

Eligible individuals should be identified in each of the database using a pre-specified selection process and/or by applying pre-specified algorithms. Attrition diagrams should be made. Follow-up time should start at the moment that the latest of the inclusion criteria is met, follow-up ends at the earliest of the occurrence of censoring conditions or the last data draw down/data availability.

Study period, study population and follow-up period for signal evaluation study designs are summarized in **Table 3**.

Note to future investigators: this section provides general information and should be adapted according to the type of safety study conducted.

Table 3. Study period, study population, and follow-up period by study design

Study design/Analysis Method	Study period	Study population [§]	Follow-up period
Cohort	Index cohort: from <<COVID-19 vaccine>> introduction until last data collected Comparison cohort: from <<COVID-19 vaccine>> introduction until last data collected	Index: all subjects who received at least 1-dose of COVID-19 vaccine Comparison: all subjects matched for covariates such as age, sex, comorbidities, identified from same data source(s) who did not receive COVID-19 vaccine or alternative vaccine.	Start: latest of fulfillment of inclusion criteria or start of study period End: earliest of end of study period or censoring conditions
Case-control	From <<COVID-19 vaccine>> introduction until date protocol is implemented or data is available	Cases: Subjects with a diagnosis of << event>> in the study period. Controls: Subjects matched on age, sex, database and/or region without << event>> diagnosis at the time of index	From start of follow-up until index date The length of risk period ('look back period') should be defined according to the event under evaluation

		date. Index date = index date of the corresponding cases	
SCCS	From <<COVID-19 vaccine>> introduction until latest data available	Subject who received at least 1-dose of COVID-19 vaccine and who experienced <<event>>	Start: latest of fulfillment of inclusion criteria or start of study period End: earliest of end of study period or censoring conditions

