SCRI	From <<COVID-19 vaccine>> introduction	Subject who received at least 1-dose of COVID-19 vaccine and who experienced <<adverse event>>	Follow-up should begin on the day of vaccine exposure. Length of follow-up will be fixed and depend on the risk and control periods that may vary according to the event. Follow-up may be curtailed if censoring conditions are met.
CCO	From <<COVID-19 vaccine>> introduction	Subject who experienced << event>>	Start: after introduction of <<COVID vaccine>> in a country and other inclusion criteria and are met End: the index date of the event.

⁵Study population for pregnancy outcomes should be adapted and includes pregnant women only, specific inclusion criteria may be required.

Note to future investigators: this section provides guidance and should be adapted according to the type of study design implemented.

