9.6.2 Measures of Association

Measures of association and statistical methods for each of the signal evaluation study designs are presented in **Table 4** below.

Null hypothesis for the study will be:

- **Cohort:** H_0 : the incidence of << event >> in the index group is equal to the incidence of << event >> in the comparison group.

- **Case-Control:** H_0 : the odds of cases exposed to <<COVID-19 vaccine >> is equal to the odds of controls exposed to <<COVID-19 vaccine>>.
- **Self-controlled:** H_0 : the incidence of << event>> in the risk period is equal to the incidence of << event>> in the control period.

Table 4. Measures of association according to the type of study design

Study design	Events	Statistical method	Measures of association
Cohort	All events excluding pregnancy outcomes	Poisson regression or Cox regression (time-dependent covariates/exposure)	Rate ratio or Hazard ratio
	Pregnancy outcomes	Binomial or logistic regression	Prevalence or odds ratio
Case-Control/Case cross over	All	Conditional logistic regression	Odds ratio
Self-controlled	All	Conditional Poisson regression	Incidence Rate Ratio

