Event temporarily decreases or increases likelihood of vaccination	✓	✓	✓	✓	✓
Event is a (permanent) contraindication to vaccination	O ^b	O ^b	O ^b	O ^b	✓
Event censors the period of observation for exposure (e.g., death or an outcome that increases the probability of death such as myocardial infarction)	✓	✓	X	X	✓
Event is independently recurrent	✓	✓	✓	✓	✓
Event is non-recurrent but rare	✓	✓	✓	✓	✓
Event is recurrent, and recurrent events are not independent (e.g., stroke)	✓	✓	O ^c	X	O
Temporal trends in vaccination					
Temporal trends in vaccination are not present during the study period	✓	✓	✓	✓	✓
Temporal trends in vaccination are present during the study period	✓	✓	✓	✓	O

Checkmark indicates design is suitable; X indicates not suitable; O indicates that the study design is possible under certain circumstances.

^a Suitable if prodromal symptoms before diagnosis of the outcome do not cause or prevent vaccination, either temporarily or permanently. To address this potential source of bias, every effort should be made to identify the onset of symptoms from the available data such as medical records, rather than relying on the date of diagnosis.

^b Suitable if the vaccine is given in a single dose. If the vaccine is given in multiple doses, the design is not suitable unless special analytic techniques are applied to handle censored, perturbed, or curtailed post-event exposures.

^c Suitable if appropriate adaptations to the self-controlled case series are applied (Farrington, 2010)

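### SCRI follow-up may be cut at any censoring condition, with no exemption for death or exit caused by the event, which pulls the rate ratio towards safety

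*Protocol*

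**What the plan says.** The SCRI row of Table 3 (protocol, section 9.2.2) makes two statements in sequence: "Length of follow-up will be fixed and depend on the risk and control periods that may vary according to the event", and then "Follow-up may be curtailed if censoring conditions are met". The text above the table gives the rule for all designs, without the word *may*: "follow-up ends at the earliest of the occurrence of censoring conditions or the last data draw down/data availability". Neither place lists the censoring conditions or separates exits caused by the event from unrelated ones.

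Three other places determine what curtailment does:

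- Section 9.1.3.2 defines the SCRI control window as "a pre-specified time window occurring after the risk window". There is no control time before vaccination. The note to Figure 4 reads "Example with a risk period of 42 days and a control period of 42 days".
- Table 4 (section 9.6.2) assigns "Conditional Poisson regression" to the self-controlled designs.
- The Annex 3 decision framework marks SCRI as not suitable under the criterion "Event censors the period of observation for exposure (e.g., death or an outcome that increases the probability of death such as myocardial infarction".

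Table 2, which gives the event-by-event recommendations, marks SCRI unsuitable for death and sudden death. It ticks SCRI, without a footnote, for acute respiratory distress syndrome, acute cardiovascular injury (including coronary artery disease), coagulation disorder (including pulmonary embolus and stroke) and meningoencephalitis.

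**The concern.** In a conditional analysis each case is compared only with itself, so a case informs the estimate only if it has both risk time and control time. Here control time always comes second. If the event kills the patient, or makes the patient leave the database, and follow-up stops there, the effect depends on when the event happened:

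- Event in the risk window, death before the control window opens: no control time, a constant likelihood, and the case is lost.
- Event in the risk window, death inside the control window: the case stays, with a shortened control window.
- Event in the control window, then death: the case stays with its full risk window and a shortened control window, so the event appears to have arisen in less control time than was planned.

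The first and third patterns lower the IRR, and the net effect was downward in every scenario with event-related death that was run. In a vaccine safety study that is the direction of false reassurance, and it falls on the most serious cases.

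**Working it through.** The protocol gives no sample size, effect size, case fatality or time to death for this design, so there is no figure of its own to reproduce. The check measures the bias that the rule produces.

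**Inputs from the protocol.** Risk window 42 days and control window 42 days (note to Figure 4), control window after the risk window (section 9.1.3.2), conditional Poisson model (Table 4), follow-up cut at death (section 9.2.2).

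**Assumptions, not in the protocol.** The proportion *f* of events that are fatal is the same in both windows. Time from event to death is immediate, or exponential with a mean of 7 or 14 days. Events are uniform within each window.

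**Step 1: a case that can be solved by hand (immediate death).** With true IRR ρ, a share p = ρ/(1+ρ) of cases falls in the risk window. Fatal risk-window cases vanish. Fatal control-window cases keep a control time uniform between 0 and 42 days. The estimate θ solves

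p(1−f) = (1−f)·θ/(1+θ) + (1−p)·f·θ·ln(1+1/θ).

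For ρ = 2 and f = 0.10 the left side is 0.600. At θ = 1.757 the right side is 0.9 × 0.6373 + 0.0333 × 0.792 = 0.5736 + 0.0264 = 0.600. So 2 becomes about 1.76. For ρ = 3 and f = 0.10 the same equation gives about 2.65.

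**Step 2: cases lost when death takes a mean of 7 days.** The chance that a fatal risk-window case dies before day 42 is 1 − (7/42)(1 − e^(−6)) = 0.83. The share of all risk-window cases lost is 0.83 × 0.10 = 8% at 10% fatality and 0.83 × 0.30 = 25% at 30%.

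**Step 3: estimate when death takes a mean of 7 days** (1,000,000 simulated cases per scenario; solving the expected score equation numerically agrees to about 0.01).

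| Fatality | True IRR 1 | True IRR 2 | True IRR 3 |
|---|---|---|---|
| 0% | 1.00 | 2.00 | 3.00 |
| 5% | 0.94 | 1.89 | 2.85 |
| 10% | 0.88 | 1.78 | 2.69 |
| 20% | 0.76 | 1.56 | 2.36 |
| 30% | 0.65 | 1.34 | 2.04 |

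With a mean of 14 days and 30% fatality, a true IRR of 2 gives 1.42.

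**Step 4: planned windows kept after event-related death.** The true value returns in every scenario (1.00, 2.00, and 2.99 to 3.01).

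**Step 5: exit unrelated to the event.** Cutting follow-up at exit gives 1.00 for a true IRR of 1, and 2.01 and 1.99 for a true IRR of 2 at exit rates of 0.002 and 0.01 per day, although up to about 20% of risk-window cases lose all control time. Curtailment is correct here. Ignoring such exit is what biases. If a share *x* exits over the 84 days at a constant rate, the IRR is multiplied by 1/√(1−x). At 0.002 and 0.01 per day, x is about 15% and 57%, and a true IRR of 2 becomes 2.18 and 3.04. At x = 1% the factor is 1.005, and at x = 5% it is 1.026.

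Steps 4 and 5 together show that the remedy must reach event-related exit and nothing else.

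**The case against.** **Annex 3 already excludes the harmful case.** It marks SCRI unsuitable where the event censors observation or raises the probability of death. If that criterion were applied consistently, little would remain. It is not: Table 2, which an investigator would consult for a named event, ticks SCRI for several potentially fatal events. Annex 3 shows that the hazard was recognised, but the follow-up rule carries no matching safeguard. The sensitivity analyses in section 9.6.5 do not cover it.

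**The sentence is permissive template text.** The SCRI row says *may*, and notes around Table 3 ask investigators to adapt the section. That softens the point. But the general rule in the same section has no *may*, and nothing tells the investigator when curtailing does harm.

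**The size is assumed.** This stands. At 5% fatality the loss is modest, and at zero there is none.

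**Stronger readings that the protocol does not support.** A reader might infer that any death or departure after vaccination biases the SCRI estimate. Step 5 shows otherwise for exit unrelated to the event. A reader might also infer that windows should be shortened only at the administrative end of data. That would override section 9.2.3.2, which censors at subsequent doses of a single-dose vaccine, and would ignore unrelated exit. Counting time after a further dose as control time can itself mask a risk. If every case were redosed on day 14 and both doses carried an IRR of 3 for 42 days, the control window would hold 14 days at threefold risk and 28 at baseline, and the estimate would be 126/(42+28) = 1.8.

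**Conclusion.** The point holds for death or exit caused by the event. As written, section 9.2.2 with the post-risk control window and the conditional Poisson model understates the IRR whenever such exits occur within the planned windows.

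With 42-day windows and a mean of 7 days to death, the understatement for a true IRR of 2 is about 6% at 5% fatality (1.89), 11% at 10% (1.78) and 33% at 30% (1.34). Slower death reduces it somewhat. These sizes rest on assumed fatality and timing. The downward direction was the same in every scenario with event-related death.

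A reader might also infer that the vaccine would always look protective when there is no effect. That follows only if some cases die of the event: at zero fatality a true IRR of 1 is estimated as 1.00. Censoring at a subsequent dose was not simulated, and no bias is claimed for it.

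Separately, Table 2 and Annex 3 disagree on whether SCRI suits events that raise the probability of death.

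**What to change.** 1. In the SCRI row of Table 3, add wording such as: *Death or exit that follows and is attributable to the event does not shorten the windows; for these cases the planned risk and control windows are kept as offsets. Follow-up is curtailed for the end of data, for subsequent doses as in section 9.2.3.2, and for exit unrelated to the event.* Make the general rule above the table refer to this exception.
2. In section 9.6.5, add a sensitivity analysis: where the cause of exit is unclear, report the estimate with the windows kept and with the windows curtailed.
3. Reconcile the SCRI column of Table 2 with the Annex 3 criterion for the potentially fatal events, by changing the entries or by a footnote stating the condition for use.

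The cost is a few sentences and the work of classifying some exits. Unrelated exit wrongly treated as event-related pushes the IRR up. Even if all of it were misclassified, the rise would be about 0.5% at 1% exit over 84 days (1/√0.99) and about 2.6% at 5% (1/√0.95). Both exit rates are assumptions.

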9.2.3 Variables

9.2.3.1 Event Assessment

In this section, the operational definitions for identifying each <<event>> should be described, with reference to code lists included in a separate protocol appendix.

Definitions, codes, and proposed algorithms for all AESI can be found at https://drive.google.com/drive/folders/1Y_3cuGRN1g-jBv2ec1fC0aYcpxEjtrY9. These AESI definition templates can serve as example for event definitions forms for non-anticipated events.

Note: The AESI event definitions forms documents will be evolving based on experience in the calculation of background rates in the ACCESS project (EUPAS37273).

<<Event>> should be identified in each participating database using diagnosis codes, where possible algorithms should be used to ascertain the event or for sensitivity analyses. Performance of algorithms should be benchmarked by comparing incidence rates with published rates and between databases as described in ADVANCE (Sturkenboom, 2020). The provenance of diagnosis codes (e.g. hospital vs. general practice) should be considered in development and application of event algorithms (Gini, 2019).

For signal evaluation studies event identification algorithms should be validated using chart abstraction or manual verification of electronic records while being blinded to the <<COVID-19 vaccine>> exposure. If resources are restricted a sample may be validated initially to assess the positive predictive value (PPV). If the PPV is below 80% all cases should be validated.

Certainty of the diagnosis of an event should be classified against the existing and new Brighton Collaboration (BC) case definitions. SPEAC is providing a toolbox to those case definitions which is accessible from the Brighton Collaboration website or by writing to the [contact]. Analysis may be restricted to specific BC level cases for case-based analyses, whereas sensitivity analyses and cohort incidence estimations may focus on inclusion of lowest level of diagnostic certainty.

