9.1.1 Cohort

Retrospective (multi)-database cohort study where index <<COVID-19 vaccinated>> subjects and reference (subjects not vaccinated with << COVID-19 vaccine>>: reference cohort) are compared for occurrence of << event>>.

The comparison cohort will be matched using as example frequency matching or propensity score matching for important covariates such as age, sex and comorbidities (including COVID-19 infection prior to reference date) and markers of health care utilization (Austin, 2011). The comparison cohort could be the following:

- A concurrent comparison cohort including subjects not vaccinated with <<COVID-19 vaccine>> at the time of study start, identified at the same date (+/- 7 days – eg. anchored on a healthcare visit or pharmacy dispensing) of the exposure date (1st vaccine dose in case of multi-dose vaccine) of the matched vaccinated subjects. This calendar date time matching will allow to control for the variation in the SARS-CoV2 circulation and will minimize the risk of immortal time bias given that the time period before vaccination is immortal. To test for the presence and magnitude of immortal time, the time

difference between cohort entry and the date of start of vaccine distribution should be calculated for each cohort member and the frequency distribution of immortal time compared between the vaccinated and unvaccinated cohorts.

- If <<COVID-19 vaccine>> is distributed concurrently with the seasonal influenza vaccine, persons receiving both <<COVID-19 vaccine>> and the seasonal influenza vaccine could be compared with those receiving the influenza vaccine alone.
- A comparison cohort including subjects vaccinated with alternative <<COVID-19 vaccine>> in the same week as the matched index subjects. This time matching will allow to control for the variation in the SARS-CoV2 circulation.
- In the instance where the risk period of <<event>> is well known, the comparison cohort may be the same persons as the index cohort, with the comparison person time chosen after the ending of the risk window. Time trends in events cannot be controlled for in this manner.

[figure not shown]
The incidence rate ratio of the <<event>> is calculated comparing the incidence rate in index with that in the comparison cohort. The required follow-up time will depend on the event under evaluation, this follow-up time should take into account the vaccination schedule (**Figure 1**).

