9.4 Study Size

[figure not shown]
[To be completed by the study investigator(s) based on assumptions of number of cases and effect estimate size at the time of the full protocol development]

For signal evaluation studies sample size calculations should be conducted that would allow ability to detect risk with the highest precision. The sample size will be driven by the background rate of the event under evaluation and the size of the data source(s).

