Case -control studies using health care data sources have the advantage of having recorded vaccination prior to case occurrence. Matching and restriction should be applied to deal with confounding. Main sources of bias could be selection bias (e.g. validation cannot be performed for all cases) and is related to exposure, or if validation is conducted in an unblinded manner.

The main strengths of self-controlled designs are the adjustment for time-invariant covariates and their suitability to assess acute events. For less acute events and long latency events, a long washout period will be required and any uncertainty about risk periods will lead to misclassification and attenuation of risk estimates. A major limitation of the CCO is that it should not be used if there are temporal trends in exposure.

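### The 80% PPV rule tests the level of PPV but not whether it differs between the groups or windows compared, so a study can meet it with a biased rate ratio

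*Protocol*

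**What the plan says.** Section 9.2.3.1 (Event Assessment) sets this requirement for the evaluation of a signal: "event identification algorithms should be validated using chart abstraction or manual verification of electronic records while being blinded to the <<COVID-19 vaccine>> exposure". Investigators with limited means may review only some of the cases at first, to estimate the PPV. The decision rule follows: "If the PPV is below 80% all cases should be validated". By implication, at 80% or above the remaining cases may be analysed without validation.

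This is the only PPV criterion in the protocol. It is ordinary text rather than a bracketed placeholder, so a study built on the template will carry it over unless someone changes it. No section asks for PPV by vaccination status or by risk versus control window.

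The measures that depend on the flagged events are relative ones. For the cohort design, Section 9.1.1 states: "The incidence rate ratio of the <<event>> is calculated comparing the incidence rate in index with that in the comparison cohort". Table 4 in Section 9.6.2 gives an odds ratio for the case-control design and an incidence rate ratio for the self-controlled designs.

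**The concern.** An algorithm can be right four times in five overall and still be right more often in one group than in the other. False-positive events then inflate one side of the comparison more than the other, and the ratio moves away from its true value even though the overall PPV looks acceptable.

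Blinded review keeps the reviewer's judgement independent of exposure. It does not affect which patients were given the code in the first place, so it cannot make the algorithm equally accurate in both groups.

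The other checks do not fill the gap. Benchmarking in Section 9.2.3.1 compares incidence with published rates and between databases, not by exposure. The sensitivity analyses in Section 9.6.5 cover risk windows, event dates and time-varying confounders. The note in Section 9.7 asks for code counts and rates over time and by database. None of these would show a PPV difference between the groups compared.

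At stake is a safety evaluation that shows a spurious excess, or hides part of a real one, while correctly reporting that its validation criterion was met.

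**Working it through.** **Inputs.** From the protocol: the 80% threshold, the sampling option and the blinded review (Section 9.2.3.1), and the rate ratio as effect measure (Section 9.1.1). Not in the protocol: PPV in each group, the vaccinated share of flagged cases, and the validation sample size. Section 9.4 leaves study size to be completed "based on assumptions of number of cases and effect estimate size". There is therefore no stated figure to reproduce, and every split below is an assumption.

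**Formula.** With sensitivity S in a group, flagged events = S × true events / PPV. Dividing the vaccinated by the comparator rate gives

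RR(observed) = RR(true) × [S(vaccinated)/S(comparator)] × [PPV(comparator)/PPV(vaccinated)].

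With equal sensitivity the middle term is 1, and the bias factor is PPV(comparator)/PPV(vaccinated).

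The overall PPV is w × PPV(vaccinated) + (1 − w) × PPV(comparator), where w is the vaccinated share of flagged cases. For a gap d = PPV(comparator) − PPV(vaccinated) and an overall PPV of 0.80, PPV(vaccinated) = 0.80 − (1 − w)d.

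**Overall PPV 0.80 (rule met), w = 0.5:**

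| Gap | PPV vaccinated | PPV comparator | Bias factor |
|---|---|---|---|
| 0 | 0.800 | 0.800 | 1.000 |
| 5 points | 0.775 | 0.825 | 1.065 |
| 10 points | 0.750 | 0.850 | 1.133 |
| 20 points | 0.700 | 0.900 | 1.286 |
| 20 points, reversed | 0.900 | 0.700 | 0.778 |

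**Dependence on w, 20-point gap, overall PPV 0.80.** At w = 0.3 the split is 0.66/0.86 (vaccinated/comparator) and the factor 0.86/0.66 = 1.303. At w = 0.7 it is 0.74/0.94 and 0.94/0.74 = 1.270. Reversed, the factors are 0.74/0.94 = 0.787 and 0.66/0.86 = 0.767. The result depends little on w in this range.

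**A higher overall PPV does not remove it.** At overall PPV 0.90 and w = 0.5, a split of 0.85/0.95 gives 1.118 and a split of 0.80/1.00 gives 1.250.

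**What the rule itself rules out.** At overall PPV 0.80 and w = 0.5, the most extreme split is 0.60/1.00, so the threshold confines the factor only to 0.600 to 1.667. These are arithmetic limits, not expected values.

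**Other designs.** In a case-control study the same factor applies to the odds of vaccination among cases. In the SCCS and SCRI every case is vaccinated, so the relevant ratio is PPV(control window)/PPV(risk window).

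**The case against.** Several objections carry weight. Full validation is the default, and sampling is allowed only when resources are restricted. The text says simply the PPV: that it is one figure pooled over exposure groups is an inference from the absence of any requested split, and nothing shows that databases are meant to be pooled. The note in Section 8 lets investigators modify the wording. Bias needs a real PPV difference, and the protocol gives no evidence of one. The formula assumes equal sensitivity, and anything that prompts extra coding after vaccination could change sensitivity too. These points limit the size of the concern, but the rule as written still never examines the quantity that determines the bias.

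A reader might infer more than the protocol supports:

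- **That the protocol itself concedes differential coding accuracy.** Section 9.8 says of case-control studies: "Main sources of bias could be selection bias (e.g. validation cannot be performed for all cases) and is related to exposure". That concerns which cases can be validated, not whether codes are less accurate in one exposure group.
- **That the rule contradicts the Brighton Collaboration provisions.** Section 9.2.3.1 adds "Analysis may be restricted to specific BC level cases for case-based analyses" and says that "sensitivity analyses and cohort incidence estimations may focus on inclusion of lowest level of diagnostic certainty". Both are optional. The request to classify diagnostic certainty is not confined to sampled cases, and an investigator who restricts by level can classify the cases used. There is no contradiction.
- **That small samples will often pass by chance.** This depends on sample sizes that the protocol does not give and may properly leave to the full protocol or analysis plan.

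**Conclusion.** The concern holds in a limited form. The 80% rule controls the level of PPV, whereas bias in the rate ratio comes from its difference between the groups or windows compared, and no other provision of the protocol checks that difference. Under equal sensitivity, an overall PPV of 80% and half of flagged cases vaccinated, a 5-point gap shifts the ratio by about 6%, a 10-point gap by about 13%, and a 20-point gap by about 29% upward or 22% downward. These are illustrations and not estimates for any vaccine or event. If the PPVs are equal there is no bias. The protocol does not show that such differences will occur, only that its rule would not detect them. The change is worth making because it mainly alters how a sample that is already foreseen is drawn and read.

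**What to change.** Reword the rule in Section 9.2.3.1 as follows.

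1. Draw the validation sample stratified, within each database, by exposure group (cohort, case-control) or by risk versus control window (self-controlled designs). Someone other than the reviewer makes the selection, so that the review stays blinded.
2. Report PPV with its confidence interval for each stratum.
3. Keep the 80% trigger on the observed PPV, but apply it in each exposure group or window.
4. Where sampling is accepted, report as a sensitivity analysis RR(corrected) = RR(observed) × PPV(vaccinated)/PPV(comparator), with the window-specific equivalent for self-controlled designs and an interval that includes the uncertainty in both PPVs.
5. Validate all cases if the PPVs clearly differ, by a criterion that the investigators set in advance.

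For the assumed 0.70/0.90 split, step 3 would send all cases to validation, and the correction gives 1.286 × 0.70/0.90 = 1.00. Step 3 alone is not enough: with both PPVs between 0.80 and 1.00, the factor can still lie anywhere from 0.80 to 1.25. Steps 4 and 5 deal with that remainder.

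**Cost.** Protocol wording, a stratified draw, a less precise corrected ratio, and somewhat more frequent full validation. As an illustration with assumed sizes, suppose that the true PPV is 90% in both groups and 25 cases are reviewed per group. Each group passes with binomial probability P(X ≥ 20; n = 25, p = 0.90) = 0.967, so both pass with probability 0.967² ≈ 0.93. A single sample of 50 passes with probability P(X ≥ 40; n = 50, p = 0.90) = 0.99. At a true PPV of 85% the figures are 0.838² ≈ 0.70 and 0.88.

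A stricter criterion, requiring the lower confidence limit to reach 80% in each group, is not recommended. With 25 per group, an exact 95% limit needs 25 of 25 confirmed. At a true PPV of 90%, both groups would pass with probability 0.90^50 ≈ 0.5%, which would in effect remove the sampling option.
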